## 1. INTRODUCTION

This statistical analysis plan (SAP) lays out key elements including definitions and statistical methods for analysis of data in evaluation of efficacy and safety for the PCYC-1142-CA study. Analyses of pharmacokinetics (PK) data and exploratory analyses such as for clonal evolution and disease-related mechanisms of resistance will be addressed in separate documents.

Throughout this SAP, “study treatment” and “study drug” are used interchangeably.

### 1.1. Study Design

This is an international multicenter, 2-cohort Phase 2 study assessing both minimal residual disease (MRD)-guided discontinuation and fixed duration (FD) therapy with the combination of ibrutinib + venetoclax (‘Ibr + Ven’ hereafter) in subjects with treatment-naïve chronic lymphocytic leukemia (CLL) or small lymphocytic lymphoma (SLL). Figure 1 outlines the study design.

The MRD cohort begins with the same 15-cycle treatment (3 cycles of ibrutinib single agent lead-in followed by 12 cycles of Ibr + Ven) as in the FD cohort. This is followed by 1 cycle of Ibr + Ven during which MRD-guided randomization occurs, after which treatment proceeds according to the randomization. MRD negativity is assessed by a central laboratory and defined as  $<1$  CLL cell per 10,000 leukocytes ( $<1 \times 10^{-4}$ ), as assessed by flow cytometry of a peripheral blood (PB) or bone marrow (BM) aspirate sample. MRD negativity for randomization purposes must be confirmed serially over at least 3 cycles and must be negative in both bone marrow and peripheral blood.

The randomized treatment for MRD cohort starts from cycle 17 day 1. MRD-negative randomized subjects are randomized to receive double blind ibrutinib or placebo and to be treated until MRD relapse or disease progression (PD) or unacceptable toxicity. MRD-positive randomized subjects are randomized to receive open label ibrutinib or ibrutinib + venetoclax: ibrutinib is to be continued until PD or unacceptable toxicity in either arm, while venetoclax can be administered for up to 2 years cumulatively (including pre-randomization and randomization phases) or until PD or unacceptable toxicity, whichever the earliest.

The FD cohort is an open-label, 1 arm cohort with a fixed duration 15-cycle treatment: 3 cycles of ibrutinib single agent lead-in followed by 12 cycles of Ibr + Ven. This cohort was added in Protocol Amendment 1 after the completion of MRD cohort enrollment. Each cycle consists of 28 days.

All subjects who discontinue treatment in the absence of disease progression will remain on response follow-up until confirmed PD or until study closure. After PD, subjects will be followed for survival and subsequent anti-cancer therapies. Treatment reintroduction is allowed per investigator’s discretion for both cohorts as following:

For MRD cohort, treatment reintroduction is allowed for both arms of MRD-negative randomized subjects after MRD-positive relapse and/or PD and for ibrutinib arm only for MRD-positive

[figure not shown]

randomized subjects after PD. For placebo subjects, ibrutinib is to be reintroduced first and venetoclax may be added further if subsequently PD on reintroduced ibrutinib. Ibrutinib subjects (either MRD-negative randomized or MRD-positive randomized) may continue ibrutinib and reintroduce venetoclax treatment. Reintroduced venetoclax can be administered for up to 2 years.

For FD cohort, subjects with PD after completion of the 15-cycle fixed duration treatment may be retreated by, per investigator's discretion, either continuous single agent ibrutinib until PD or unacceptable toxicity, or a repeat of the fixed duration 15-cycle treatment (3 cycles of ibrutinib single agent lead-in followed by 12 cycles of Ibr + Ven).

Investigators and an independent review committee (IRC) perform the response assessments independently based on radiological imaging, physical examination or other procedures as necessary, hematology results, disease-related symptoms and bone marrow examinations (where appropriate). The response evaluations are in accordance with the International Workshop on Chronic Lymphocytic Leukemia (IWCLL) guidelines (Hallek 2008) including subsequent clarifications (Hallek 2012, Hallek 2013, Cheson 2012).

**Figure 1. Study Design**

## 1.2. Endpoints

MRD Cohort	FD Cohort
Primary Endpoint 
 
1-year disease-free survival (DFS) rate in MRD-negative randomized subjects
 
	Primary Endpoint 
 
Complete response (CR/CRi) rate
 

Secondary Endpoints 
 
MRD negativity rate
 
Overall response rate
 
Complete response rate (CR / CRi)
 
Duration of response
 
TLS risk reduction
 
Progression free survival
 
Overall survival
 
	Secondary Endpoints 
 
Duration of response
 
MRD negativity rate
 
Overall response rate
 
TLS risk reduction
 
Progression free survival
 
Overall survival
 

Safety Assessments 
 
Safety and tolerability
 
	Safety Assessments 
 
Safety and tolerability
 

Exploratory Endpoints 
 

 
	Exploratory Endpoints 
 

 

## 1.3. Statistical Hypotheses

### MRD Cohort

The primary objective of this cohort is to evaluate if discontinuing ibrutinib, in the setting of a confirmed MRD-negative response with the combination of ibrutinib + venetoclax (I+V), allows for a treatment holiday as assessed by 1-year disease-free survival.

The statistical hypotheses are as follows:

$H_0$ : The DFS rate at 1-year landmark for experimental treatment group,  $S_I(1)$ , is equal to the control group,  $S_C(1)$ :

$$S_I(1) = S_C(1)$$

versus

$H_1$ : The DFS rate at 1-year landmark for experimental treatment group,  $S_I(1)$ , is different from the control group,  $S_C(1)$ :

$$S_I(1) \neq S_C(1)$$

These hypotheses will be tested at 2-sided  $\alpha$  level of 0.05 using z test for the difference of two proportions based on Kaplan-Meier estimates with standard error of each arm computed using Greenwood's formula.

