2. STUDY OBJECTIVE

2.1. Primary Objective

MRD Cohort

- To evaluate if discontinuing ibrutinib, in the setting of a confirmed MRD-negative response with the combination of ibrutinib + venetoclax (I+V), allows for a treatment holiday as assessed by 1-year disease-free survival. 1-year disease-free survival is defined as continued MRD-negative response without progression or death at least one year after randomization.

Fixed Duration Cohort

- To evaluate the depth of response with the combination of ibrutinib + venetoclax (I+V) administered for a fixed duration of therapy by assessment of complete response (CR/CRi) rate.

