## **1.4. Sample Size Determination**

### **MRD Cohort**

The MRD cohort is powered based on the primary endpoint of randomization phase, 1-year DFS rate in MRD-negative randomized subjects (ibrutinib vs placebo). The total sample size will be based on both MRD negativity rate from the Pre-randomization Phase and the sample size assumption from Randomization Phase.

Sixty randomized subjects with confirmed MRD negativity will provide approximately 80% power to detect a 30% improvement in the 1-year disease-free rate, assuming the 1-year disease-free rate is 60% for the control (placebo) arm, at a 2-sided significant level of 0.05.

Assuming a 40% MRD negativity rate for the ibrutinib and venetoclax combination therapy in the Pre-randomization Phase, 150 subjects will be enrolled in the Pre-randomization Phase in order to have 60 subjects achieve confirmed MRD negativity and to be randomized.

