### 1.5. Planned Analysis

#### 1.5.1. Interim Analysis

No interim analysis was planned or performed for the randomization period of the MRD cohort or for the FD cohort. The protocol prespecified analyses for pre-randomization phase of MRD cohort were completed as follows:

The safety of Ibr + Ven regimen was assessed in safety run-in subjects (the first 14 enrolled MRD cohort subjects) by Data Review Committee (DRC) consisting of the Medical Monitor or designee, a Drug Safety representative, a biostatistician, and at least 2 participating Investigators. DRC meetings were held first on 01May2017 and then on 07Nov2017 when the 6th and the last (i.e. the 14th) safety run-in subjects, respectively, completed the dose limiting toxicity (DLT) evaluation period (defined as the 5-week venetoclax dose ramp-up in combination with ibrutinib plus an additional week of follow up) respectively. No DLT or TLS occurred in safety run-in subjects. The DRC recommended for the study treatment regimen to move forward without modification in both meetings.

To ensure adequate sample size in the MRD-negative randomization, an early assessment of the MRD negativity rate with Ibr + Ven was performed when the first 30 subjects completed 9 cycles of treatment (6 cycles Ibr + Ven) as of the 30Mar2018 data extraction. MRD negativity in PB was achieved in 23 subjects, rate 77% (95% exact binomial confidence interval [CI]: 58% - 90%). The first 14 subjects also completed MRD testing in both PB and BM at cycle 16 as needed to assess for confirmed MRD negative status. Confirmed MRD negativity was achieved in 11 of 14 subjects, rate 79% (95% exact binomial CI: 49% - 95%). The sample size assumption was confirmed, and enrollment continued as planned (section 1.4).

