## 1.6. Testing Procedure and Level of Significance

For both cohorts, hypothesis testing will be performed independently (without multiplicity adjustment) for the primary endpoint only. Other endpoints will be summarized descriptively with 95% confidence interval (CI) whenever applicable.

- Primary endpoint for MRD cohort, 1-year DFS rate in MRD-negative randomized subjects, will be tested between placebo and ibrutinib arms at a 2-sided alpha level of 0.05.
- Primary endpoint for FD cohort, CRR, will be tested in non-del 17 subjects at a 1-sided alpha level of 0.025.

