**Table 2: Definitions and Analyses for Endpoints**

Endpoint	Definition	Analysis Method
Primary Endpoint for MRD Cohort (Not Applicable for FD cohort)		
1-year DFS rate in MRD-negative randomized subjects	DFS will be analyzed in MRD-negative randomized subjects and is defined as time from randomization date to MRD-positive relapse [1], or disease progression per investigator assessment or death from any cause, whichever occurred first. Subjects who do not experience any DFS event will be censored by the last MRD sample date with a valid result [2] or the date of last adequate disease assessment [3] after randomization, whichever occurs earlier. If no valid MRD result and no adequate disease assessment after randomization, DFS will be censored on the randomization date.	
Primary
 
The 1-year DFS rates will be estimated using Kaplan-Meier method and the corresponding 2-sided 95% CI will be provided. Z test for the difference of two proportions will be performed based on Kaplan-Meier estimates with standard error of each arm computed using Greenwood's formula.
 
Supportive
 
A log-rank test will be performed for between-arm comparison of DFS distribution. The hazard ratio and its 95% CI based on Cox regression model will be calculated. The 2-year DFS will be explored when median follow-up post randomization <math>\geq 2</math> years.

Endpoint	Definition	Analysis Method
Primary Endpoint for FD Cohort (Secondary Endpoint for MRD cohort)		

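### SAP Table 2 does not stratify the supportive DFS log-rank test and Cox model by IGHV, the randomisation factor; as a minor addition, it should list a CI for the between-arm difference in 1-year DFS.

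*SAP*

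**What the plan says.** **Objective and primary test.** Protocol 2.1 asks whether stopping ibrutinib "allows for a treatment holiday as assessed by 1-year disease-free survival". SAP 1.3 repeats the objective, whether "discontinuing ibrutinib, in the setting of a confirmed MRD-negative response with the combination of ibrutinib + venetoclax (I+V), allows for a treatment holiday", and tests equality of the two 1-year DFS rates at 2-sided 0.05 with a "z test for the difference of two proportions based on Kaplan-Meier estimates with standard error of each arm" from Greenwood's formula. SAP 1.4 gives 60 randomised subjects about 80% "power to detect a 30% improvement in the 1-year disease-free rate", from 60% on placebo. SAP 1.6 states that "hypothesis testing will be performed independently (without multiplicity adjustment) for the primary endpoint only".

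**Estimates listed.** Table 2 of the SAP says: "The 1-year DFS rates will be estimated using Kaplan-Meier method and the corresponding 2-sided 95% CI will be provided". It adds a supportive log-rank test and a Cox hazard ratio with 95% CI. It lists no CI for the difference between the two 1-year rates. The DFS endpoint itself is "defined as time from randomization date to MRD-positive relapse [1], or disease progression per investigator assessment or death from any cause".

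**IGHV.** SAP 1.7.2 stratifies each randomisation scheme by IGHV (unmutated against mutated, the latter including borderline or not evaluable). Protocol 10.4 says that stratified analyses will use this factor, without saying which analyses those are. Protocol 1.1.1 describes IGHV status as an important prognostic factor. Table 2 mentions no stratification for the log-rank test or the Cox model, and SAP section 6, on changes from the protocol's analyses, is silent on it.

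**The concern.** When randomisation is stratified by a factor expected to be prognostic, the natural between-arm comparison respects the strata. A pooled log-rank test then discards some information, and an unadjusted Cox hazard ratio mixes subjects with different baseline risk. Because the documents do not say whether these two analyses are stratified, the choice would be made at analysis, possibly after the arms are known.

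The second matter is how the primary result will speak to the objective. A significant result in favour of ibrutinib counts against a holiday. A non-significant one does not establish a holiday, because the p-value does not show how large a loss from stopping remains compatible with the data. A CI for the difference does show that, and it is on the scale of the primary endpoint.

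**Working it through.** **1. The plan's own power figure.** Inputs from SAP 1.4 and 1.7.2: 30 per arm (60 randomised 1:1), 60% against 90%, 2-sided 0.05. With arm-specific standard errors, SE = sqrt(0.6×0.4/30 + 0.9×0.1/30) = 0.1049. Power = Φ(0.30/0.1049 − 1.96) = 81.6%. Exact binomial enumeration of the same test gives 82.2%. The stated figure of about 80% reproduces, with the 30% improvement read as 30 points.

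**2. Effect of stratifying the log-rank test.** The documents give no stratum-specific rates, so these inputs are assumptions: two equal IGHV strata, exponential times, one year of follow-up, and a placebo-to-ibrutinib hazard ratio of ln 0.75 / ln 0.90 = 2.73 (which turns 90% into 75%). With 60,000 replicates, the simulation standard error near 34% power is sqrt(0.34×0.66/60,000) = 0.002.

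| Ibrutinib 1-year DFS by stratum | Per arm | Unstratified power | Stratified power |
|---|---|---|---|
| 90% / 90% (not prognostic) | 30 | 0.341 | 0.339 |
| 94% / 86% (moderate) | 30 | 0.326 | 0.335 |
| 97% / 80% (strong) | 30 | 0.318 | 0.369 |
| 90% / 90% | 59 | 0.586 | 0.586 |
| 94% / 86% | 59 | 0.572 | 0.586 |
| 97% / 80% | 59 | 0.587 | 0.641 |

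Under the null, rejection rates were 0.049 to 0.053 stratified and 0.043 to 0.054 unstratified. The strong-case gain varies with the set-up, including small arm imbalances within a stratum, so it is best quoted as about 3 to 5 points.

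**3. What a non-significant primary result would mean.** Exact enumeration of the unpooled z test, ibrutinib 90%, no censoring before 1 year. The losses are illustrations, not limits taken from the documents. SAP 1.5.1 reports confirmed MRD negativity in 11 of 14 subjects (CI 49% to 95%). Applied to all 150 enrolled, that gives 150×(11/14)/2 ≈ 59 per arm, with a range of 150×0.49/2 ≈ 37 to 150×0.95/2 ≈ 71.

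| Per arm | Non-significant, true 15-point loss | Non-significant, true 20-point loss |
|---|---|---|
| 30 | 0.634 | 0.461 |
| 37 | 0.583 | 0.387 |
| 59 | 0.395 | 0.192 |
| 71 | 0.331 | 0.132 |

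At 30 per arm, the 15-point figure is 0.538 if the ibrutinib rate is 95% and 0.686 if it is 85%.

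**4. What the CI adds.** Suppose 27/30 on ibrutinib and 22/30 on placebo are disease-free. The difference is −16.7 points, SE = sqrt(0.9×0.1/30 + 0.733×0.267/30) = 0.0976, p = 0.088, and the CI is −16.7 ± 1.96×9.76, or −35.8 to +2.5 points. The p-value alone would hide that range.

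**The case against.** The strongest reply is that the primary analysis is already adequate. Table 2 pre-specifies the placebo-arm 1-year DFS rate with a CI, which is the direct estimate of outcome off drug, and a hazard ratio with a CI. The z test already computes the difference and its standard error, so anyone can form the interval. This stands: no information is lost, and the CI request is a matter of reporting.

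A reader might infer that the sponsor plans to treat p > 0.05 as proof that a holiday is safe. No section says so. The SAP sets out a test for a difference and attaches no conclusion to a null result. The non-significance rates above show why an interpretive sentence is useful; they do not show an error in the plan.

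On IGHV, a reader might infer that the SAP breaks a protocol commitment. It does not: Protocol 10.4 names the factor without assigning it to any particular analysis. It is also fair that the log-rank and Cox analyses are only supportive, that the unstratified test keeps acceptable size, and that the gain is small unless IGHV is strongly prognostic. What remains is that stratifying matches the design, has essentially no downside, and settles a choice now left open.

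The larger per-arm numbers are fragile. They rest on 14 subjects, and Protocol 3.1.1 bars subjects who have stopped ibrutinib from randomisation.

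**Conclusion.** The point holds as a modest improvement to supportive analyses, plus a minor reporting addition. Stratifying the log-rank test and Cox model by IGHV costs nothing beyond simulation error (0.2 points at most in the table) when IGHV is not prognostic, and it gains about 0 to 1 or 3 to 5 points when IGHV is moderately or strongly prognostic. These figures rest on the assumed equal strata, exponential times and hazard ratio.

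Non-rejection of equality would be weak evidence for a holiday at the planned size, and still not strong at the larger sizes that the early MRD results suggest. That rests on a 90% ibrutinib rate and no early censoring.

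The result does not extend to the stated power, which is correct, or to the choice of primary test. Nor does a gap in DFS equal a gap in progression or death: DFS events include MRD-positive relapse without clinical progression, and SAP 1.1 allows ibrutinib to be reintroduced in placebo subjects.

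**What to change.** Before the MRD-cohort data are summarised by arm:

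1. In SAP Table 2, state that the supportive log-rank test and Cox model are stratified by IGHV status as randomised, using the two categories in SAP 1.7.2.
2. In the same row, add the placebo-minus-ibrutinib difference in 1-year DFS with its 2-sided 95% CI, from the Greenwood standard errors already used in the z test.
3. Add one sentence saying that failure to reject equality is not evidence of similarity, and that the holiday objective will be discussed from this CI and the placebo-arm rate, noting that DFS includes MRD-positive relapse.

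Leave the z test, its alpha and the sample size unchanged.

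The cost is a few lines of SAP text, with no extra subjects or data. The one consequence to accept is that a non-significant result with a wide interval would have to be reported as inconclusive. If both arms are at 90%, the half-width is 1.96×sqrt(0.18/n): 15.2 points at 30 per arm and 10.8 at 59.

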### **FD Cohort**

The primary hypothesis of this cohort is that: Complete response rate (CRR) is  $> 37\%$  after 12-cycle Ibr + Ven treatment.

The statistical hypotheses are as follows:

$$H_0: \text{CRR} \leq 37\%$$

versus

$$H_1: \text{CRR} > 37\%$$

These hypotheses will be tested at 1-sided  $\alpha$  level of 0.025 using asymptotic test for the binomial proportion. Since the assumption for sample size and power of this cohort is based on the historical data of subjects without del 17p, the formal hypothesis testing will be performed on the non-del 17p population (section 2).

## **1.4. Sample Size Determination**

### **MRD Cohort**

The MRD cohort is powered based on the primary endpoint of randomization phase, 1-year DFS rate in MRD-negative randomized subjects (ibrutinib vs placebo). The total sample size will be based on both MRD negativity rate from the Pre-randomization Phase and the sample size assumption from Randomization Phase.

Sixty randomized subjects with confirmed MRD negativity will provide approximately 80% power to detect a 30% improvement in the 1-year disease-free rate, assuming the 1-year disease-free rate is 60% for the control (placebo) arm, at a 2-sided significant level of 0.05.

Assuming a 40% MRD negativity rate for the ibrutinib and venetoclax combination therapy in the Pre-randomization Phase, 150 subjects will be enrolled in the Pre-randomization Phase in order to have 60 subjects achieve confirmed MRD negativity and to be randomized.

## FD Cohort

In the FD cohort, assuming the complete response rate for Ibr + Ven is 50%, 125 subjects without del 17p will provide 83% power to ensure the rate is > 37% at 1-side alpha 0.025. A CR rate of 50% would represent meaningful improvement compared to the CR rate seen with the fixed duration combination of bendamustine + rituximab (31%), and would be an improvement over the CR rate seen with the standard of care fixed duration regimen fludarabine, cyclophosphamide and rituximab (40%) which were obtained in the CLL10 study, which included only patients without del 17p (Eichhorst 2016).

The sample size and power calculations were calculated using the software package, East (Cytel Software Corp, Cambridge, MA) version 6.3.

### 1.5. Planned Analysis

#### 1.5.1. Interim Analysis

No interim analysis was planned or performed for the randomization period of the MRD cohort or for the FD cohort. The protocol prespecified analyses for pre-randomization phase of MRD cohort were completed as follows:

The safety of Ibr + Ven regimen was assessed in safety run-in subjects (the first 14 enrolled MRD cohort subjects) by Data Review Committee (DRC) consisting of the Medical Monitor or designee, a Drug Safety representative, a biostatistician, and at least 2 participating Investigators. DRC meetings were held first on 01May2017 and then on 07Nov2017 when the 6th and the last (i.e. the 14th) safety run-in subjects, respectively, completed the dose limiting toxicity (DLT) evaluation period (defined as the 5-week venetoclax dose ramp-up in combination with ibrutinib plus an additional week of follow up) respectively. No DLT or TLS occurred in safety run-in subjects. The DRC recommended for the study treatment regimen to move forward without modification in both meetings.

To ensure adequate sample size in the MRD-negative randomization, an early assessment of the MRD negativity rate with Ibr + Ven was performed when the first 30 subjects completed 9 cycles of treatment (6 cycles Ibr + Ven) as of the 30Mar2018 data extraction. MRD negativity in PB was achieved in 23 subjects, rate 77% (95% exact binomial confidence interval [CI]: 58% - 90%). The first 14 subjects also completed MRD testing in both PB and BM at cycle 16 as needed to assess for confirmed MRD negative status. Confirmed MRD negativity was achieved in 11 of 14 subjects, rate 79% (95% exact binomial CI: 49% - 95%). The sample size assumption was confirmed, and enrollment continued as planned (section 1.4).

### 1.5.2. Primary Analysis

The primary analysis for the MRD cohort will be performed after the last randomized subject has the opportunity to receive 1 year of randomized treatment. All safety and efficacy endpoints for MRD cohort will be analyzed at the time of the primary analysis.

The primary analysis for FD cohort will be performed after the last enrolled FD subject has the opportunity to be followed for at least 30 cycles (15 cycles of treatment + 15 cycles of post-treatment follow-up). All safety and efficacy endpoints for FD cohort will be analyzed at the time of the primary analysis. A longer-term analysis for selected MRD cohort endpoints will also be performed using the same data extraction.

The CSR of this study will describe analyses of both MRD and FD cohorts based on data extracted at the time of FD cohort primary analysis. Results for the primary analysis of MRD cohort with earlier data extraction will also be summarized in a report and be documented in the appendix of clinical study report (CSR).

